9.3 CRITERIA FOR REMOVAL FROM PROTOCOL TREATMENT

Subjects may discontinue study treatment at any time. Any subject who discontinues treatment will be asked to return to the study center to undergo end of treatment assessments as outlined within Study Calendar (Section 7.2). The primary reason for discontinuation should be recorded. In the absence of treatment delays due to adverse events, treatment may continue until one of the following criteria applies:

- Radiographic disease progression
- Clinical disease progression

- Inter-current illness that would, in the judgment of the investigator, affect assessments of clinical status to a significant degree or require discontinuation of study drugs
- Completion of protocol treatment.
- Unacceptable toxicity
- Death
- Subject may withdraw from the study at any time for any reason.
- Treatment delay for unacceptable duration for any toxicity in the opinion of the investigator
- Concomitant treatment with a prohibited medication
- Subject non-compliance

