9.4 DURATION OF FOLLOW UP

Subjects may be followed for survival status every 3 months for up to 6 months after the last patient on study visit (LPV) at the investigator's discretion.

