10.2 SECONDARY EFFICACY ENDPOINTS

1) **Duration of response** (DOR) as measured from the date of first response (CR or PR) to date of disease progression (taking as reference for progressive disease the smallest measurements recorded since the treatment started) or death.

2) **Disease control rate** (DCR) based on patient who had CR or PR or Stable disease (SD) for at least 2 cycles (8 weeks).

3) **Best overall response** (BOR) determined from a sequence of responses assessed. Two objective status determinations of CR before progression are required for a BOR of CR. Two determinations of PR or better before progression, but not qualifying for a CR, are required for a BOR of PR. A minimum timeframe of 8 weeks is required for a BOR of SD.

3) **Progression free survival** (PFS) as measured from the date of first study drug dose to the date of the first objective documentation of radiographic disease progression or death due to any cause.

4) **Overall survival** (OS) as measured from the date of first study drug dose to the date of death by any cause.

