11.2.3 ANALYSIS OF THE SECONDARY EFFICACY ENDPOINT(S)

Disease control rate (DCR) is defined as the proportion of patients who achieve a CR or PR or SD for at least 2 cycles. DCR will be summarized for the ITT population using frequencies and proportions. A 95% CI for the DCR will be constructed using exact binomial (Clopper-Pearson) methods.

Best overall response (BOR) will be determined from a sequence of responses assessed. Two objective status determinations of CR before progression are required for a BOR of CR. Two determinations of PR or better before progression, but not qualifying for a CR, are required for a BOR of PR. A minimum timeframe of 8 weeks is required for a BOR of SD. BOR will be summarized for the ITT population using frequencies and proportions. A 95% CI for BORs of CR, PR, SD or PD will be constructed using exact binomial (Clopper-Pearson) methods.

Duration of response (DOR) will be evaluated only for responders. Duration of response is measured from the date of first confirmed response (CR or PR) to date of first disease progression (taking as reference for progressive disease the smallest measurements recorded since the treatment started) or death. DOR will be summarized graphically using Kaplan-Meier curves. Median DOR and corresponding 95% CI will be reported. For patients who are not known to have died or to have had a progression of disease as of the data-inclusion cut-off date, DOR will be censored at the date of last objective response assessment prior to the date of any subsequent systemic anticancer therapy.

Progression free survival (PFS) is defined as the time from the date of start of treatment to the first date of radiologically documented progressive disease or the date of death due to any cause, whichever occurs first. PFS will be summarized graphically using Kaplan-Meier curves. Median

PFS and corresponding 95% CI will be reported. For patients who are not known to have died or progressed as of the data-inclusion cut-off date, PFS time will be censored at the date of the last objective progression-free disease assessment prior to the date of any subsequent systemic anticancer therapy.

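### Clinical progression ends treatment but is not a PFS event, and no text expressly continues scans after treatment stops, so PFS, and DOR on a measurement-based reading, will tend to read too long

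*Combined protocol and SAP*

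**What the plan says.** Section 9.3 gives separate reasons for ending treatment. Besides radiographic progression, they include "Clinical disease progression" and "Unacceptable toxicity". The primary reason for stopping is to be recorded.

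The PFS event is narrower. Section 10.2 defines it as the "first objective documentation of radiographic disease progression or death due to any cause", and 11.2.3 as the "first date of radiologically documented progressive disease or the date of death due to any cause, whichever occurs first". Clinical progression is in neither definition.

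The censoring rule in 11.2.3 is that "PFS time will be censored at the date of the last objective progression-free disease assessment" before any new systemic anticancer therapy. The rule is conditional: "For patients who are not known to have died or progressed as of the data-inclusion cut-off date, PFS time will be censored".

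The DOR event in 11.2.3 is the "date of first disease progression (taking as reference for progressive disease the smallest measurements recorded since the treatment started) or death". It refers to measurements but does not use the word radiographic.

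Scans are every 8 weeks from Cycle 1 Day 1 (6.1, 7.1.6, 9.2). Section 7.1.6 keeps them on schedule when dosing changes, but it deals with missed doses and does not mention patients who have stopped. For the period after treatment, 9.4 says: "Subjects may be followed for survival status every 3 months", at the investigator's discretion.

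**The concern.** A patient who deteriorates clinically between scans can leave treatment with no radiographic progression on file. The plan has no analysis rule for that patient. It does not say whether clinical progression counts as having progressed for the censoring rule, and no sensitivity analysis addresses it.

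Such censoring is informative. Patients whose disease has just worsened leave the risk set as event-free, and the Kaplan-Meier estimate treats them as having the same outlook as those who remain. If a later death is captured, the patient does have an event, but it is dated at death and not at progression. Both routes lengthen PFS, and DOR too on the measurement-based reading. A reader comparing the result with published PFS figures would see a more favourable number than the patients' course supports.

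**Working it through.** **The plan's own figures.** The plan states no assumed median, event count or follow-up time for PFS or DOR, so there is nothing on this point to reproduce.

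**Inputs from the documents.** Scans every 8 weeks; PFS event is radiographic progression or death; censoring at the last progression-free assessment; expansion cohort of up to 12.

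**Assumed inputs, not in the documents.** Exponential time to progression with median M = 4 months (3 months as a second case). Clinical-only share of progressions f = 10%, 20%, 30%, 40%. Median time from clinical progression to death 3 months, where deaths are captured. No scan after a clinical stop.

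**Step 1: true value.** The scan interval is 56 / 30.4375 = 1.84 months, so 24 weeks is 5.52 months. The chance of passing one interval without progression is p = 0.5^(1.84/4) = 0.727, and q = 1 − p = 0.273. True 24-week PFS is 0.727³ = 0.384.

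**Step 2: no deaths captured.** Clinical-only progressors are censored at the previous scan. The risk set at the next scan is then a fraction 1 − fq of those who entered the interval, of whom p are progression-free. Kaplan-Meier survival per interval is p / (1 − fq), and 24-week PFS is its cube. For f = 30%: 0.727 / (1 − 0.3 × 0.273) = 0.792, and 0.792³ = 0.497.

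**Step 3: every death captured.** Reported PFS is (1 − f) × 0.384 + f × P(T + D > 5.52), where T is time to progression and D is time from progression to death. With rates a = ln2/4 = 0.173 and b = ln2/3 = 0.231, P = (b·e^(−5.52a) − a·e^(−5.52b)) / (b − a) = 0.699. For f = 30%: 0.7 × 0.384 + 0.3 × 0.699 = 0.479.

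| Clinical-only share f | True 24-week PFS | Reported, no deaths captured | Reported, all deaths captured | Expected patients of 12 if all progress (12f) |
|---|---|---|---|---|
| 10% | 0.384 | 0.418 | 0.416 | 1.2 |
| 20% | 0.384 | 0.455 | 0.447 | 2.4 |
| 30% | 0.384 | 0.497 | 0.479 | 3.6 |
| 40% | 0.384 | 0.544 | 0.510 | 4.8 |

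**Step 4: the median.** It moves in 8-week steps. With M = 4 and every progression dated at the next scan, survival is 0.529 at week 16 and 0.384 at week 24, so the median reads 24 weeks. With censoring as in Step 2 it is still 24 weeks at f = 10%, 20% and 30%, and 32 weeks at 40%. With M = 3 it stays at 16 weeks for f = 10% and 20% and moves to 24 weeks at 30%, where survival at week 16 is 0.532 instead of 0.427.

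**Step 5: effect of the supportive analysis.** If clinical progression counts as an event on its date, all progressions up to week 24 are counted by week 24. The estimate returns to 0.384 for every f.

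**Step 6: toxicity stops.** Simulated toxicity stops independent of progression risk left the median at 3.98 months against a true 4.0, which is no bias. The other possible route is response confirmation. The rule in 11.1 declares the trial negative at 1 response in 12 and may call the combination promising at 2. The posterior probabilities stated there, 16% and 42%, recompute to 15.5% and 41.5%.

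**The case against.** Death is an event for PFS and DOR, and the censoring rule excludes anyone known to have died. A reader might infer from the rule that the sickest patients are simply censored. The text does not support that: a patient stopped at week 14 is censored at week 8 only if there is no later scan and no death is captured. Optional survival follow-up makes this possible but not automatic. The bias survives the objection in smaller form, because a captured death still dates the event too late (Step 3).

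A reader might also infer that no scan is required after treatment. That would be a reading of silence. The 8-week schedule has no stated end, and the tumor assessment row of the calendar cannot be read reliably in the available text. Censoring is tied to new systemic therapy, not to stopping study drug, so off-treatment scans already count where they exist. What stands is that nothing expressly calls for them.

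A third tempting reading is that toxicity stops inflate PFS as well, with the 34.8% QTc figure in 3.1.7 as a measure of scale. Neither part is supported. Censoring at a toxicity stop biases PFS only if the stop is linked to progression risk, and 34.8% is an event rate. Under 6.5.4 many such events lead to dose reduction or no change, not discontinuation.

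Finally, PFS and DOR are secondary and descriptive, and no decision rests on them. With 12 patients the standard error near 0.38 is √(0.384 × 0.616 / 12) = 0.14, about the size of the largest shift shown. That limits the stakes. It does not excuse a systematic error in a known direction that is cheap to expose. Radiographic progression or death is a conventional definition and can remain the main analysis.

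**Conclusion.** The point holds for clinical progression. Followed as written, and with no later scan obtained, the plan gives a PFS that reads too long whether or not the death is captured. For DOR the same follows only if progression there is read as measurement-based, which is a reasonable inference but not stated.

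Under an assumed 4-month exponential median and a 10% to 40% clinical-only share, 24-week PFS reads about 0.42 to 0.54 against 0.38, or 0.42 to 0.51 with all deaths captured. The reported median often does not change. The clinical-only share, the median and the time to death are assumptions, so the documents do not fix the size for this trial.

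Toxicity stops are not shown to bias PFS. Their possible effect is that a first PR may lack a clearly required confirming scan. That could matter because the decision turns on 1 versus 2 responses in 12, but its size cannot be set from the documents.

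**What to change.** In 11.2.3, add a supportive PFS and DOR analysis that counts treatment stopped for clinical progression as an event on that date. Report it beside the main analysis, together with the reasons for censoring. Section 9.3 already has the primary reason for discontinuation recorded.

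In 9.2 and 9.4, state that patients who stop treatment without radiographic progression keep the 8-week assessments until radiographic progression, new systemic therapy, death or withdrawal of consent. Accept standard-of-care scans, and state that these scans may confirm a response.

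The cost is protocol and analysis wording, a few follow-up scans and a slightly shorter reported PFS. The supportive analysis also brings in an investigator-judged event in an open-label trial, which is why it should sit beside the main analysis and not replace it.

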11.2.4 SAFETY ANALYSES

All patients in the safety analysis set will be evaluated for safety and toxicity. Adverse events, SAEs and TEAEs will be summarized by System Organ Class (SOC) and by decreasing frequency of Preferred Term within SOC. Safety analyses will include the following summaries:

- AEs, including severity and possible relationship to study drug
- SAEs, including possible relationship to study drug
- AEs leading to dose adjustments
- DLTs and DLT-E events
- Discontinuations from study treatment due to AEs or death
- Treatment-emergent abnormal changes in laboratory values
- Treatment-emergent abnormal changes in vital signs and ECGs

AEs should be reported for 28 days after the last dose of tarloxotinib and/or sotorasib.

11.2.5 EXPLORATORY ANALYSES

The frequency and proportion of patients with specific mutations and alterations will be summarized. Corresponding exact binomial (Clopper-Pearson) 95% confidence intervals will be constructed. The association of specific mutations and alterations with clinical activity will be evaluated using Fisher's exact test for categorical efficacy endpoints and using Cox proportional hazards regression models for time-to-event efficacy endpoints.

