10.4 EXPLORATORY ENDPOINTS

- 1) To evaluate the utility of detection of KRAS G12C mutations in plasma ctDNA to identify the study population.
- 2) To explore the association between baseline tumor biomarkers, gene alterations and clinical activity.
- 3) To identify known and possibly new markers of resistance to KRAS G12C inhibition in baseline tumor tissue (if available) including phosphorylated ERK and S6 kinase.
- 4) To examine mutations in *RAS* and other tumor genes potentially implicated in the resistance to sotorasib using ctDNA.

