11 STATISTICAL CONSIDERATIONS

11.1 STUDY DESIGN

Study CTO # 103048 is a potentially multicenter, non-randomized, single cohort phase IB trial evaluating the safety and efficacy of tarloxotinib in combination with sotorasib in NSCLC patients with KRAS G12C mutation who have progressed on any small molecule KRAS G12C inhibitor.

Safety lead-in

A minimum of 6 patients and as many as 18 patients will be enrolled in a safety lead-in cohort to evaluate the safety of the combination of tarloxotinib and sotorasib. Sotorasib will be held at a fixed dose of 960 mg QD (the approved dose) while the starting dose of tarloxotinib will be the monotherapy RP2D equal to 150mg/m² QW (dose level 1 [DL1]). Following a 3+3 algorithm, an initial 3 patients will be enrolled at DL1. If 0 or 1 of 3 patients experience a DLT, an additional 3 patients will be enrolled to DL1. DL1 will be declared the combination RP2D (RP2D_c) if at most 1 of 6 patients treated at DL1 experience a DLT. Alternatively, if there are 2 or more DLTs observed at DL1, 3 patients will be enrolled at DL -1 and the 3+3 rules repeated for safety evaluation. The RP2D_c will be the highest DL at which at most 1 patient of 6 experiences a DLT. If DL -2 is considered too toxic, additional dose levels below DL -2 to be determined may be considered for safety.

Dose expansion

Once the tarloxotinib RP2D_c is reached, an expansion cohort of up to 12 patients will be enrolled to evaluate the safety of the combination of tarloxotinib and sotorasib. Eligible safety lead-in patients treated at the RP2D_c will be included in the expansion cohort.

The combination of tarloxotinib and sotorasib will not be considered promising if there is weak evidence the true objective response rate (ORR) exceeds 20%. Specifically, the trial will be declared negative if $\text{Prob}(\text{true ORR} > 20\% | \text{observed no. of responses}) < 20\%$, equivalent to observing at most 1 response in 12 patients. We assume the true ORR follows a beta (0.5, 0.5) prior distribution and, conditional on the true ORR, the number of responses follows a binomial distribution. If at least 2 responses in 12 patients are observed, the combination may be considered promising. Given 1 response in 12 patients, the probability the true ORR exceeds 20% is approximately 16%. Given 2 responses in 12 patients, the probability the true ORR exceeds 20% is approximately 42%.

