11.2.2 ANALYSIS OF THE PRIMARY EFFICACY ENDPOINT(S)

Objective response rate (ORR), defined as the proportion of patients who achieve a best overall response of CR or PR, is the primary efficacy endpoint. Tumor response will be measured and recorded using RECIST 1.1 guidelines (Eisenhauer et al. 2009). All lesions should be radiologically evaluated using the same method used for baseline evaluation. Any CR or PR will require confirmation at least 4 weeks following initial response observation. Objective response rate will be summarized for the ITT population using frequencies and proportions. A 95% CI for the ORR will be constructed using exact binomial (Clopper-Pearson) methods.

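### With 1–2 responses in 12, the planned Fisher test on objective response cannot flag a resistance marker carried by 8 or fewer patients; adding best percent change in tumor size would be a cheap, more sensitive exploratory outcome

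*Combined protocol and SAP*

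**What the plan says.** Section 10.4 lists as an exploratory aim "To explore the association between baseline tumor biomarkers, gene alterations and clinical activity". It also aims to find resistance markers in baseline tissue, where available, and to examine resistance mutations in ctDNA.

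Section 11.2.5 begins descriptively: "The frequency and proportion of patients with specific mutations and alterations will be summarized", with exact intervals. It continues: "The association of specific mutations and alterations with clinical activity will be evaluated". The same sentence gives the method: associations are to be "evaluated using Fisher's exact test for categorical efficacy endpoints and using Cox proportional hazards regression models for time-to-event efficacy endpoints". No alpha, sidedness, marker list, prevalence, power or multiplicity rule is given.

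The categorical efficacy endpoints are ORR (yes/no), DCR (yes/no) and BOR (CR, PR, SD, PD), from Sections 11.2.2 and 11.2.3. On numbers, Section 11.1 says that "an expansion cohort of up to 12 patients will be enrolled" and that "Eligible safety lead-in patients treated at the RP2D_c will be included in the expansion cohort", so efficacy rests on about 12 patients. The trial is negative at 0 or 1 response, and "If at least 2 responses in 12 patients are observed, the combination may be considered promising".

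Section 11.2.2 states that "Tumor response will be measured and recorded using RECIST 1.1 guidelines", and Section 6.1 schedules imaging every 8 weeks. No section analyzes percent change in lesion size as an outcome.

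**The concern.** RECIST response is a cut of a measured quantity. The cut is the right basis for the primary ORR, but nothing in the documents requires it for the marker analysis. With 12 patients and very few responders, the resulting 2×2 table has few possible configurations, and often none of them is extreme enough to give a small p-value.

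The stake is interpretation. A trial that looks for resistance markers could report no association with response when the test could not have shown one. A patient with 29% shrinkage and a patient with clear growth would both count simply as non-responders in that table.

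A smaller gap lies alongside. Section 10.4 names phosphorylated ERK and S6 kinase, which may be graded, while Section 11.2.5 specifies tests only for mutations and alterations.

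**Working it through.** **Plan's own figures.** With a beta(0.5, 0.5) prior and r responses in 12, Prob(ORR > 20%) = 1 − BetaCDF(0.20; 0.5 + r, 12.5 − r). This gives 0.155 for r = 1 and 0.415 for r = 2, matching the stated 16% and 42%. So 1 and 2 responses are the counts on either side of the plan's decision line.

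**Smallest attainable Fisher p.** Take n = 12, m carriers and r responders, none of whom carries the marker. This is the most extreme resistance table. Its probability is C(12 − m, r)/C(12, r). The two-sided p adds any equally or less likely table in the other tail. Two-sided 0.05 is my assumption.

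- r = 1: the best case is m = 11, p = 1/12 = 0.083. The 0.05 level is never reached.
- r = 2, C(12, 2) = 66: m = 10 gives 1/66 = 0.015; m = 9 gives 3/66 = 0.045; m = 8 gives 6/66 = 0.091; m = 7 gives 10/66 = 0.152; m = 6 gives 2 × 15/66 = 0.455. For m = 5 and m = 4 the two-sided values are 0.470 and 0.515.
- r = 3, C(12, 3) = 220: m = 7 gives 10/220 = 0.045; m = 6 gives 2 × 20/220 = 0.182.
- r = 4, C(12, 4) = 495: m = 7 gives 5/495 = 0.010; m = 6 gives 2 × 15/495 = 0.061.
- r = 5 and r = 6: 0.05 can be reached from m = 5 upward (0.028 and 0.015).

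So with 1–2 responses no marker with 8 or fewer carriers reaches 0.05 in the resistance direction, and with 3–4 responses none with 6 or fewer does.

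**The other direction.** If both of 2 responders carry the marker, 2 carriers give 0.015 and 3 carriers give 0.045. The limit above is specific to resistance markers.

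**Other planned tests.**

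- Fisher on DCR with 6 of 12 controlled and full separation: 5 carriers give 0.015 and 6 give 0.002.
- Exact (Freeman-Halton) test on BOR with 2 PR, 5 SD and 5 PD, 4 carriers all PD: 0.020.
- Cox on PFS with 12 events, equal split and Schoenfeld's formula: Φ(√(12 × 0.25) × ln HR − 1.96) = 22% at HR 2 and 48% at HR 3.

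**Wilcoxon on best percent change.** With full separation and no ties the smallest two-sided p is 2/C(12, m) for m up to 6: 0.167 (m = 1), 0.030 (2), 0.009 (3), 0.004 (4), 0.002 (6). It does not depend on the number of responders.

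**Power by simulation.** Assumptions: n = 12, normal best percent change with equal SD, carriers shifted 1.5 SD toward growth, cut-points solved for pooled ORR 20% and DCR 60%, and every patient measured.

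| Carriers | Wilcoxon | Fisher, ORR | Fisher, DCR |
|---|---|---|---|
| 3 | 44% | 0.1–0.2% | 33% |
| 6 | 58% | 2% | 17% |
| 9 | 43% | 35% | 8% |

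For BOR with 6 carriers, at the same shift and an assumed DCR of 50–80%, the exact unordered test had 10–27% power. At 9 carriers and shifts of 1.0 to 2.0 SD, Wilcoxon leads Fisher on ORR by only about 3 to 13 points.

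**The case against.** The strongest reply is that the plan does not confine Fisher's test to response yes/no. It covers DCR and four-level BOR as well, and both can reach significance with only 2 responders. That stands. A reader might infer that the biomarker analysis as planned can almost never detect anything, and the documents do not support this. The sharp limit belongs to objective response, in the resistance direction, at low response counts or with minority markers.

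Three related inferences also go too far:

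- That a gain of tens of points is general. Every patient has already progressed on a KRAS G12C inhibitor, so a common resistance marker cannot be excluded. With 9 carriers the gain over Fisher on ORR is small.
- That the tumor measurements go unused. They determine response category, DOR and PFS, and PFS enters the Cox models. Only percent change as an outcome is missing.
- That the exploratory aims cannot be answered. The aims on resistance markers in tissue and in ctDNA are largely descriptive, and Section 11.2.5 provides frequencies and intervals.

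It is also fair that these analyses are exploratory, with no stated alpha, power claim or decision rule, so nothing in the plan is miscalculated.

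Percent change has its own weaknesses. Section 4.1 admits evaluable-only disease, so some patients will have no target-lesion sum. A patient can also shrink and still progress through a new lesion. The simulation's complete, normal data favor Wilcoxon. These points call for ranking rules. They do not remove the advantage seen in the scenarios run, where Wilcoxon had higher power than each Fisher test.

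**Conclusion.** The point holds in limited form and with low severity. At 1–2 responses in 12, Fisher's test on objective response cannot reach 0.05 for a resistance marker carried by 8 or fewer patients. At 3–4 responses the bound is 6 or fewer carriers. This part is exact enumeration and rests only on n = 12 and the assumed two-sided 0.05. If fewer than 12 patients have tissue, the set of possible tables shrinks further.

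The power comparison is conditional. Marker prevalence, shift size, DCR and normality are all assumptions, because the documents give none of them. Under a 1.5 SD shift the gain over the better of Fisher on ORR and DCR is about 41 points with 6 carriers (58 − 17), 11 with 3 (44 − 33) and 8 with 9 (43 − 35). The primary ORR analysis, the 2-of-12 rule, RP2D selection and safety monitoring are not affected.

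**What to change.** In Section 11.2.5:

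- Add best percent change from baseline in the sum of target-lesion diameters as a tumor-activity outcome for biomarker associations. Use an exact Wilcoxon rank-sum test for present/absent alterations and Spearman correlation for graded markers such as phosphorylated ERK and S6 kinase.
- For BOR, use an exact test that respects the order CR, PR, SD, PD.
- Give the worst ranks to patients who progress or die without a post-baseline scan. State in advance how patients who progress by new or non-target lesions are ranked. Include patients without measurable target lesions through ordered BOR only.
- Keep the Fisher tables for ORR and DCR, and leave the primary ORR analysis and the 2-of-12 rule as they are.

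The cost is SAP wording and a little more analysis code. No new data are needed for patients with measurable disease, because the lesion sums already underlie RECIST response. The downside is that percent change will be missing for patients with evaluable-only disease.
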